APPENDIX V: INFORMED CONSENT FORM

A template informed consent form will be provided under separate cover.

Clinical Investigation Plan

APPENDIX VI: MONITORING PLAN

A copy of the Monitoring Plan can be obtained upon request from the Sponsor for the clinical investigation.

Clinical Investigation Plan

APPENDIX VII: CASE REPORT FORMS

A copy of sample Case Report Forms can be obtained upon request from the Sponsor for the clinical investigation.

Clinical Investigation Plan

APPENDIX VIII: GRID ELECTRODE CONFIGURATIONS

HD Wave Electrode Configuration

For the purposes of this clinical study, HD Wave electrode configuration will be considered any configuration that only utilizes mapping data collected at electrodes with orthogonal bi-poles. Orthogonal bi-poles are defined as a pair of perpendicular bi-poles originating from a single electrode with one bi-pole configured across two separate splines and one bi-pole configured along the spline. Automap settings will be set to select the 'best duplicate' at each electrode with orthogonal bi-poles.

An example of GRID with HD Wave configuration is depicted in **Figure 3**. This HD Wave configuration utilizes bi-poles both along each spline of the catheter (A, B, C, and D) and across GRID catheter splines (A-B, B-C, and C-D) as depicted by the dark arrows. Bipolar electrogram voltages along the splines are configured as in the along-the-spline configuration described below; using electrode pairs 1-2, 2-3, and 3-4 on each spline. Bipolar electrogram voltages across the splines are recorded using electrode pairs of the same number/position on adjacent splines (A1-B1, B1-C1, C1-D1, A2-B2, B2-C2, C3-D3, A3-B3, B3-C3, C3-D3). Automap settings will be set to select the 'best duplicate' at each electrode shown in yellow.

An alternate example of GRID with HD Wave configuration is depicted in **Figure 4**. Bipolar electrograms are configured as depicted by the dark arrows. Bipolar electrogram voltages along the splines are configured using the following electrode pairs and directionality: A1-A2, A2-A3, A4-A3, B1-B2, B2-B3, B3-B4, C2-C1, C3-C2, C4-C3, D1-D2, D3-D2, D4-D3. Bipolar electrogram voltages across the splines are configured using the following electrode pairs and directionality: A1-B1, B1-C1, D1-C1, A2-B2, B2-C2, C2-D2, B3-A3, C3-B3, D3-C3, A4-B4, C4-B4, D4-C4. Automap settings will be set to select the 'best duplicate' at each electrode shown in yellow.

Clinical Investigation Plan

[figure not shown]

Figure 3. Example of GRID HD Wave Electrode Configuration

Clinical Investigation Plan

[figure not shown]

Figure 4. Example of alternative GRID HD Wave electrode configuration

Along-the-Spline Configuration

This configuration utilizes bi-poles, or electrogram pairs, along each of the GRID catheter splines (labeled A, B, C, and D). On each spline, electrodes are numbered 1 through 4, with 1 being the most distal electrode. Bipolar electrogram voltages are recorded using electrode pairs 1-2, 2-3, and 3-4. An additional bi-pole is recorded using the shaft electrodes (S1-S2).

Clinical Investigation Plan

[figure not shown]

Figure 5. Along-the-spline GRID Electrode Configuration

Other Configurations

For the purposes of this clinical study, any electrode configuration that does not meet the definition of HD Wave or along-the-spline configuration (i.e. use of all bipoles employing a combination of electrodes with orthogonal bipoles and electrodes with only along the spline configurations) will be classified as 'other'.

Clinical Investigation Plan

APPENDIX IX: REVISION HISTORY

This CIP may be amended as appropriate by the Sponsor. Rationale will be included with each amended version in the revision history table below. The version and date of amendments will be documented.

EC and relevant Regulatory Authorities, if applicable, will be notified of amendments to the CIP.

Clinical Investigation Plan

APPENDIX X: CIP SUMMARY

Clinical Investigation Name and Number	WAVE-MAP AF
Title	High-Density Wave Mapping in Subjects with Atrial Fibrillation as a Predictor of Recurrence After a Single Ablation Procedure Using a PVI-Only Strategy
Purpose/ Objective(s)	
The primary objective of this study is to characterize low-voltage substrate, as identified via HD Wave mapping in sinus rhythm and identify associations with 12-month recurrence rates after a single pulmonary vein isolation with a contact force RF ablation catheter.
 
Other objectives of this study include:
 
 • Analyze additional maps and data collected with GRID and associations with 12-month recurrence rates, such as: 
 ◦ Voltage maps using different configurations recreated post procedure ◦ Voltage maps using different thresholds for low-voltage ◦ Fractionation maps • Collect mapping data in AF to support future research and development. • Support future study designs to identify optimal treatment approaches for individual patients.
Number of Subjects Required for Inclusion in Clinical Investigation	[REDACTED]
Clinical Investigation Design	This is a single-arm, multicenter, post-market study. There will be no randomization. The purpose of the study is to determine correlations between low-voltage substrate, as identified via HD Wave mapping, and recurrence of atrial fibrillation after a single pulmonary vein isolation with a contact force RF ablation catheter.
Primary Endpoint	The primary outcome is one-year success, defined as freedom from AF/AFL/AT after removal from antiarrhythmic drug therapy as assessed from the end of the 3-month blanking period to 12 months following a single ablation procedure.
Subject Follow-up	Subjects will have follow-up visits at 3, 6, and 12 months post ablation procedure. The 6-month visit can be conducted via telephone.
Inclusion Criteria	
 1. Documented atrial fibrillation with planned endocardial ablation procedure 2. Age 18 years or older

Clinical Investigation Plan

	
3. Able and willing to provide written informed consent prior to any clinical investigation related procedure4. Able and willing to complete all required study procedures through 12 months
Exclusion Criteria	
1. Long-standing persistent atrial fibrillation defined as continuous AF greater than 12 months in duration2. Previous ablation or surgery in the left atria3. Implanted left atrial appendage occluder4. Implanted mitral or tricuspid valve replacement5. Implanted cardiac defibrillator (ICD)6. Participation in another clinical investigation that may confound the results of this study7. Pregnant or nursing8. Presence of other anatomic or comorbid conditions, or other medical, social, or psychological conditions that, in the investigator's opinion, could limit the subject's ability to participate in the clinical investigation or to comply with follow-up requirements, or impact the scientific soundness of the clinical investigation results.9. Life expectancy less than 12 months

Clinical Investigation Plan

## 1. ACRONYMS AND ABBREVIATIONS

Acronym or Abbreviation	Complete Phrase or Definition
AAD	Antiarrhythmic Drug
AF or AFib	Atrial Fibrillation
AFL	Atrial Flutter
AT	Atrial Tachycardia
HD	High Density
LA	Left Atrium
LAA	Left Atrial Appendage
LVEF	Left Ventricular Ejection Fraction
NYHA	New York Heart Association
PVI	Pulmonary Vein Isolation
SAP	Statistical Analysis Plan

## 2. SYNOPSIS OF STUDY DESIGN

### 2.1 Purpose of the Statistical Analysis Plan

This statistical analysis plan (SAP) is intended to provide a detailed and comprehensive description of the planned analysis to be used for CRD 968 WAVE-MAP AF clinical investigation. [REDACTED]

### 2.2 Clinical Investigation Objectives

The primary objective of this study is to characterize low-voltage substrate, as identified via HD Wave mapping in sinus rhythm, and identify association with 12-month recurrence rates after a single pulmonary vein isolation (PVI) with a contact force ablation catheter. Other objectives of this study include:

- Analyze additional maps and data collected with GRID and associations with 12-month recurrence rates, such as
  - Voltage maps using different configurations recreated post procedure
  - Voltage maps using different thresholds for low-voltage Fractionation maps

i [REDACTED]

### 2.3 Clinical Investigation Design

This is a post-market, single-arm, multi-center, prospective interventional study of the Advisor™ HD Grid Mapping Catheter, Sensor Enabled™. [REDACTED]

Scheduled visits

and data collection will occur at baseline, index procedure, 3, 6 and 12-month follow up visits. Subjects will be exited from the trial at the conclusion of their 12-month follow-up visit.

### 2.4 Endpoint and Additional Data

#### 2.4.1 Primary Endpoint

The primary outcome is one-year success, defined as freedom from AF/AFL/AT after removal from antiarrhythmic drug therapy as assessed from the end of the 3-month blanking period to 12 months following a single ablation procedure.

Occurrence of isthmus-dependent atrial flutter, if confirmed during electrophysiology testing, should not be considered a failure for this outcome. This endpoint is based on the recommendations from the 2017 HRS consensus paper.

[REDACTED]

## 2.4.2 Additional Data

Additional data to be collected will include the following:

- Acute procedural success, defined as electrical isolation of all pulmonary veins.
- Success post blanking period through 12 months using different definitions, including:
  - Freedom from symptomatic AF/AFL/AT after removal from AAD therapy
  - Single procedure clinical success defined as freedom from symptomatic AF/AFL/AT without a new or increased dose of class I or III AAD
  - Freedom from AF/AFL/AT
  - Freedom from AF
- Data from EnSite maps using both HD Wave and Standard mapping modes in both sinus rhythm and AF including but not limited to:
  - Left atrial area using different boundaries (e.g. with and without LAA, etc.)
  - Low voltage area and proportion of left atria with low voltage using different cutoffs for voltage
- Rates of recurrence not due to PVI gap for subjects with repeat electrophysiology studies
- LA volume and diameter
- Adverse events including any device-, procedure-, or death-related events
- Other baseline characteristics including but not limited to:
  - Time with AF
  - Type of AF
  - Age
  - Sex
  - BMI
  - General medical history
  - Cardiovascular history
  - Arrhythmia history
  - NYHA classification
  - LVEF
  - Presence of pacemaker
  - Left ventricular hypertrophy
  - History of heart failure
- Procedural characteristics, including but not limited to:
  - Power, temperature, and contact force

- Procedure time
- Mapping time
- Cardioversions (if applicable)
- Anesthesia
- Fluoroscopy time

### **3. ANALYSIS CONSIDERATIONS**

#### **3.1 Statistical Methods**

Depending on the type of data, appropriate statistics and analyses described in the section below will be used.

##### **3.1.1 Descriptive Statistics for Continuous Variables**

Continuous (CONT) variables will be summarized with the numbers of observations, means, standard deviations, quartiles, minimums, maximums, and 95% confidence intervals for the means. When comparing HD Wave with standard mapping modes, differences in each measurement between the two modes will be summarized with the mean of the differences and its 95% confidence interval (Appendix A).

##### **3.1.2 Descriptive Statistics for Categorical Variables**

Categorical (CAT) variables will be summarized with subject counts and percentages/rates with exact 95% Clopper-Pearson confidence intervals (Appendix B).

##### **3.1.3 Survival Analyses**

Survival (SURV) analysis will be conducted to analyze time-to-event variables. Subjects without events will be censored at their last known event-free time point. Subjects withdrawn or otherwise lost-to-follow-up during the follow-up period will be censored at their last known visit. Survival data will be presented using the Kaplan-Meier product limit method. Number of subjects at risk, number of censored subjects, number of events, event free survival rate and standard error of the survival rate at each follow-up time point will be presented in a summary table.

##### **3.1.4 Logistic Regression**

Logistic regression (LOGIT) analysis will be used [REDACTED]

[REDACTED]

[REDACTED]

[REDACTED]

### **3.2 Planned Analyses**

#### **3.2.1 Analysis Populations**

##### **3.2.1.1 Enrolled Population (ENR)**

[REDACTED]

[REDACTED]

[REDACTED]

##### **3.2.1.2 Per-Treatment Evaluable Population (PTE)**

[REDACTED]

#### **3.2.2 Sample Size Calculation**

[REDACTED]

#### **3.2.3 Timing of Analysis**

Data analyses will be performed at the completion of the 12-month follow-up period for all subjects or as desired by Sponsor. In addition, study progress and data may be summarized and reported as needed.

#### **3.2.4 Endpoint and Variables for Analysis**

The following lists describe the variables and analysis methods that will be analyzed in the ENR population:

- LA volume and diameter (CONT)
- Adverse events including any device-, procedure-, or death-related events (CAT)

[REDACTED]

- Other baseline characteristics including but not limited to:
  - Time with AF (CONT)
  - Type of AF (CAT)
  - Age (CONT)
  - Sex (CAT)
  - BMI (CONT)
  - General medical history (CAT)
  - Cardiovascular history (CAT)
  - Arrhythmia history (CAT)
  - NYHA classification (CAT)
  - LVEF (CONT)
  - Presence of pacemaker (CAT)
  - Left ventricular hypertrophy (CAT)
  - History of heart failure (CAT)

The following lists describe the analysis methods for the primary endpoint and additional evaluations that will be analyzed in the PTE population:

Entity	Percentage (%)
DC	92
HI	88
IL	85
MA	84
MD	83
MN	82
NC	81
ND	80
RI	79
SD	78
VA	77
WI	75

A horizontal bar chart with 10 bars of varying lengths. The bars are black and set against a white background. The first bar is the longest, followed by a short bar, then a medium bar, then a long bar, then a short bar, then a medium bar, then a long bar, then a short bar, then a medium bar, and finally a long bar. The bars are separated by small gaps.

### 3.3 Special Analysis Issues

### 3.3.1 Handling of Missing Data

Every effort will be made to collect all required data. All data available for the endpoints specified among the analysis population will be used. Missing data will not be imputed. Kaplan-Meier analysis will censor subjects withdrawn or otherwise lost-to-follow-up at last known visit.

© 2013 Pearson Education, Inc.

### 3.3.2 Poolability Analysis

No poolability analysis will be performed.

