5.6 Number of Subjects

[REDACTED] Individual study centers will be allowed to enroll 20% (~60 subjects) of the maximum total trial enrollment without additional approval. Centers may have their maximum enrollment number increased with prior Sponsor [REDACTED]

Clinical Investigation Plan

approval. Enrollment will be limited to a maximum 110 paroxysmal AF cases, 110 early persistent AF (7 days to 3 months duration), and 110 non-early persistent AF (>3 months to 12 months duration) without Sponsor pre-approval.

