6.4 Follow-up Assessments

The following sections describe the follow-up visits and procedures. All windows are stated with respect to the index procedure unless otherwise noted. It is recommended to follow the HRS Consensus guidelines for follow-up screening depending on type of AF (e.g. paroxysmal vs. persistent). A 12-lead

⁸ This may include ablation to address the carina within the WACA circle per the investigator's discretion.

⁹ Site's standard of care is PVI-only, so no other substrate modification should be performed.

¹⁰ For example, "AF resolved to sinus rhythm during ablation of lesion #23".

Clinical Investigation Plan

ECG is recommended any time the subject returns to the clinic from 3- to 12-months post index procedure.

6.4.1 3-Month Follow Up (77 to 105 Days Post Index Procedure)

The blanking period ends on the day of the 3-month follow up visit. It is recommended the subject not be taking any class I or III AAD after the 3-month visit unless there is recurrence of AF. At the 3-month visit, the following procedures will be completed:

- Check for symptoms of recurrence
- Perform 12-lead ECG
- Document Adverse Events and Protocol Deviations
- Document AAD usage
- Document any recurrences including any details of repeat electrophysiology studies
- Instruct the subject to contact the site if they experience any symptoms of recurrence. If there are any symptoms noted after the 3-month visits through the 12-month visit, check for recurrence using 12-lead ECG or other form of monitoring per site's standard practice.

It is also recommended to provide the subject with an event monitor for recording at regular intervals (e.g. monthly) or for symptomatic events through the 12-month visit.

After the 3-month visit through the end of the study, any signs or symptoms of recurrence should be recorded, and the subject should have either a 12-lead ECG or other form of ECG monitoring per the site's standard practice to determine if recurrence has occurred.

6.4.2 6-Month (169 to 197 Days) Follow Up Phone Visit

Within two weeks of the 6-month time point post index procedure, the subject will be contacted via telephone (or seen in-clinic if standard of care) for the following assessments

- Check for symptoms of recurrence
- Document Adverse Events and Protocol Deviations
- Document AAD usage

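### The visible plan has no by-site summary and no allowance for site clustering, so its 95% intervals may be too narrow if sites differ and results are generalised beyond them

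*SAP*

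**What the plan says.** **Site differences.** SAP 3.3.2 consists of one sentence, "No poolability analysis will be performed", with no reason given. SAP 2.3 describes the design: "This is a post-market, single-arm, multi-center, prospective interventional study".

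**Site size.** Protocol 5.6: "Individual study centers will be allowed to enroll 20% (~60 subjects) of the maximum total trial enrollment without additional approval". The ceiling can move: "Centers may have their maximum enrollment number increased with prior Sponsor" approval.

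**Interval methods.** SAP 3.1.2 summarises categorical variables with "subject counts and percentages/rates with exact 95% Clopper-Pearson confidence intervals"; Protocol 8.2 limits these intervals to where the table mock-ups call for them. SAP 3.1.1 gives 95% intervals for means and for mean differences between mapping modes. SAP 3.1.3 gives Kaplan-Meier rates with standard errors. None of these shows a site term. SAP 3.3.3 says that no hypotheses will be tested.

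**What the site or operator decides.**
- Detection: for symptoms after the 3-month visit, Protocol 6.4.1 asks the site to "check for recurrence using 12-lead ECG or other form of monitoring" according to its usual practice. Event monitors are recommended, as is a 6-month Holter for persistent AF (6.4.2).
- Drugs: antiarrhythmic use during blanking follows site standard of care (6.3). Being off class I and III drugs after the 3-month visit is a recommendation (6.4.1).
- Mapping: Protocol 6.2.1 accepts any configuration that meets the HD Wave definition. It sets a dwell minimum below the recommended value, suggests the CFE Mean settings, and leaves coverage of the atrium to operator discretion.

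**What is common to all sites.** Required everywhere are 12-lead ECGs at 3 and 12 months, a 24-hour recording at 12 months, and symptom checks at 3, 6 and 12 months (6.4). Mapping and ablation follow a defined protocol and maps are read centrally (3.2).

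**What cannot be read.** The logistic regression details (SAP 3.1.4), the population definitions, the sample size and the list of methods for the primary endpoint are redacted.

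**The concern.** An interval that treats subjects as independent counts each subject as a full unit of information about the success rate. If subjects at one site resemble each other because the site monitors more, uses drugs differently or maps differently, the effective sample size is smaller than the head count. The loss grows with the number of subjects per site, so a 20% share per center matters. No hypothesis test is planned, so these intervals are the main visible statement of uncertainty.

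The second issue is confounding. The primary objective is an association between low-voltage substrate and recurrence. If sites differ both in how low voltage is captured and in how hard they look for recurrence, site affects both sides of the association, and a pooled analysis could read part of that as a substrate effect. Differences in detection can also bias the recurrence rate itself, and a wider interval does not correct bias. A table by site would at least make such differences visible.

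**Working it through.** **Inputs from the documents.** The site cap is 20%, about 60 subjects (Protocol 5.6). The confidence level is 95% and the categorical interval is Clopper-Pearson (SAP 3.1.2).

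**Assumptions (not in the documents).** Success rate p = 0.70; sites of equal size; 5, 10 or 20 sites; within-site correlation (ICC) from 0 to 0.05.

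**Step 1: implied total.** 60 / 0.20 = 300, so the plan's own pair of figures points to a maximum near 300. The three AF-type limits sum to 3 × 110 = 330, and 20% of that is 66, which does not round to 60. Those are limits by AF type, not the stated total, so 300 is used. At exactly 20% each, 1 / 0.20 = 5 sites could fill the study. That is the extreme case, not a design feature.

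**Step 2: interval ignoring site.** For 210 of 300, Clopper-Pearson gives 64.5% to 75.1%, a half-width of 5.3 points. The normal approximation gives 1.96 × √(0.70 × 0.30 / 300) = 5.2 points.

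**Step 3: design effect.** DE = 1 + (m − 1) × ICC, where m is the number of subjects per site. The half-width is multiplied by √DE. Example with m = 60 and ICC = 0.01: DE = 1 + 59 × 0.01 = 1.59; 5.19 × √1.59 = 6.5 points.

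**Step 4: actual coverage.** Site success probabilities were drawn from a beta distribution with mean 0.70 and the given ICC, outcomes were drawn within site, and the nominal 95% Clopper-Pearson interval was checked against 0.70 (100,000 replicates).

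| Sites × size | ICC | DE | Half-width (points) | Coverage |
|---|---|---|---|---|
| any | 0 | 1.00 | 5.2 | about 95.6% |
| 5 × 60 | 0.01 | 1.59 | 6.5 | 89.1% |
| 5 × 60 | 0.02 | 2.18 | 7.7 | 82.5% |
| 5 × 60 | 0.05 | 3.95 | 10.3 | 68.6% |
| 10 × 30 | 0.01 | 1.29 | 5.9 | 92.3% |
| 10 × 30 | 0.02 | 1.58 | 6.5 | 89.1% |
| 10 × 30 | 0.05 | 2.45 | 8.1 | 80.2% |
| 20 × 15 | 0.01 | 1.14 | 5.5 | 94.0% |
| 20 × 15 | 0.02 | 1.28 | 5.9 | 92.5% |
| 20 × 15 | 0.05 | 1.70 | 6.8 | 87.9% |

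To judge the ICC scale: the standard deviation of true site rates is √(ICC × 0.70 × 0.30), which is 4.6 points at 0.01, 6.5 points at 0.02 and 10.2 points at 0.05.

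**Step 5: sites treated as fixed.** If the conclusion is meant only for the enrolled sites, the between-site spread does not enter the sampling error. With five sites of 60 at true rates of 60, 65, 70, 75 and 80%, simulated coverage is 95.9%. In that reading the interval is not too narrow.

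**The case against.** The strongest reply is that the loss of coverage is conditional. It needs a positive between-site correlation and inference beyond the enrolled sites, and the documents give no ICC, site count or between-site rates. This stands, and it is why the point is worded with *may* and *if*. A reader might infer that the intervals are too narrow as a matter of fact; the documents do not support that. The fixed-sites defence is weaker here, because the stated aims reach past the enrolled sites: marketing claims (Protocol 1.0), a model to predict recurrence (1.1.1) and possible future treatment recommendations (1.1.2).

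Three other strong readings also fail:

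- *Map set-up is left to site practice.* Protocol 6.2.1 requires one mapping catheter in an HD Wave configuration and fixes the projection, interpolation, segment length and AutoMap distances for the AF map. Section 3.2 centralises the reading. Only some acquisition choices remain open.
- *Sites monitor as they please.* A minimum ECG schedule binds every site; only monitoring above it varies.
- *The SAP forbids any look at sites.* Section 3.3.2 drops a poolability analysis. It does not bar a site covariate or a descriptive table, and omitting a formal analysis is consistent with having no hypothesis tests.

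The redaction also matters. A site term in the logistic model or the primary-endpoint analysis cannot be excluded, so it would be wrong to say that the association ignores site. Such a term would not, however, change the visible interval methods or supply results by site.

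Finally, no visible decision depends on the width of the interval, and estimates of between-site variance are imprecise when sites are few. Both hold, and both argue for a sensitivity analysis and against replacing the primary intervals.

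**Conclusion.** The point holds in conditional form. The visible plan allows large sites and leaves part of detection, drug use and mapping to site or operator, but it offers no by-site results and no allowance for clustering. Under the stated assumptions, true coverage of a nominal 95% interval runs from about 69% (five sites, ICC 0.05) to 94% (20 sites, ICC 0.01). It stays at or above 95% if the ICC is 0 or if inference stops at the enrolled sites. The few-site end of that range is what Protocol 5.6 permits, not what it predicts.

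Confounding of the substrate-recurrence association by site is possible, but it is not shown, and the redacted model may already address it. The point is best classed as a cheap improvement.

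**What to change.** Replace SAP 3.3.2 with the following:

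1. A table of one-year success by site, with counts.
2. A sensitivity analysis giving the pooled one-year success rate an interval that allows for site clustering (cluster-robust or random-intercept), with a small-sample correction such as a t reference with degrees of freedom based on the number of sites.
3. Unless the redacted model already does so, a repeat of the substrate-recurrence logistic model with site as a random intercept or as a stratum, reported next to the planned estimate.

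Keep the planned intervals as primary. State whether inference is meant for the enrolled sites only or for a wider set of centers, because that decides which interval is relevant.

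Cost: SAP wording and a little programming, with no new data, since enrolment is already tracked by center. Downsides: the sensitivity interval may be wider and less favourable, and with few sites the between-site variance will be poorly estimated and should be reported as such.
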